### 7.2. Adverse Events of Special Interest

The following Adverse Events of Special Interest in mepolizumab clinical development have been defined:

- Systemic Allergic/Hypersensitivity and Non-allergic Reactions
- Local injection site reactions
- Alteration in immune response (infections)
- Alteration in immune response (malignancies)
- Alteration in cardiovascular safety
- Immunogenicity

The methods by which these events will be identified are detailed in the Program Safety Analysis Plan for Mepolizumab (PSAP), version 5 (effective 1-Apr-2019), Section 10.3.2

The details of the planned displays are provided in [Appendix 7: List of Data Displays](#).

### **7.3. Other Safety Analyses**

Details of listings of corticosteroid usage are provided in [Appendix 7: List of Data Displays](#).

## 9. APPENDICES

### 9.1. Appendix 1: Schedule of Activities

#### 9.1.1. Protocol Defined Schedule of Events

Visits and Assessments	Screening (up to 4 weeks)	Baseline	Week 4 ( $\pm$ 7 days)	Week 8 ( $\pm$ 7 days)	Week 12 ( $\pm$ 7 days)	Week 16 ( $\pm$ 7 days)	Week 20 ( $\pm$ 7 days)	Week 24 ( $\pm$ 7 days)	Every 4 week treatment cycle/assessments repeated until End of Treatment	Early withdrawal 	End of Treatment 3/ Follow-up (12 weeks post-last dose)
Application Form sent to GSK for approval	X										
Written Informed Consent	X										
Demography and CV risk assessment	X										
Eligibility assessment: inclusion & exclusion criteria review	X										
Baseline information		X									
Dosing with mepolizumab 		X	X	X	X	X	X	X			
Corticosteroid use	X	X	X	X	X	X	X	X		X	X
AE/SAE review	X	X	X	X	X	X	X	X		X	X
Urine pregnancy test (FCBP)	X	X	X	X	X	X	X	X		X	X
Documentation of Benefit:risk evaluation to support continued supply of mepolizumab 	X	X			X			X			

1. The treating physician should make a benefit:risk evaluation to confirm continued treatment with mepolizumab is appropriate prior to each administration. This will be documented every 12 weeks to support continued supply. Note: it is expected that the treating physician will monitor subjects as per standard-of-care therapy (including any requirements for blood and urine tests).
2. Safety monitoring of subjects is required during SC administration and for 1 hour after the end of the injections for the first three administrations, i.e., at baseline, and Weeks 4 and 8. From Week 12 onwards, subjects can be monitored following mepolizumab administration in accordance with standard of care at the site.
3. See Section 5.3

## 9.2. Appendix 2: Study Phases and Treatment Emergent Adverse Events

### 9.2.1. Study Phases

Treatment State	Definition
Pre-Treatment	AE Start Date/Time < Study Treatment Start Date/Time
On-Treatment	Study Treatment Start Date/Time $\leq$ AE Start Date/Time $\leq$ Study Treatment Stop Date + 28 days
Post-Treatment	AE Start Date > Study Treatment Stop Date + 28 days

**NOTES:**

- If the study treatment stop date is missing then the AE will be considered to be On-Treatment.

## 9.3. Appendix 3: Data Display Standards & Handling Conventions

### 9.3.1. Reporting Process

Software	

 
The currently supported versions of SAS software will be used.
 
	
Reporting Area	
HARP Server	CCI
HARP Compound	
Analysis Datasets	

 
Analysis datasets will be created according to CDISC standards (SDTM IG version 3.1.3 & ADaM IG version 1.0).
 
For creation of ADaM datasets (ADC1/ADAE), the same version of dictionary datasets will be implemented for conversion from SI to SDTM.
 
	
Generation of RTF Files	

 
RTF files will be generated.
 
	

### 9.3.2. Reporting Standards

General

 
The current GSK Integrated Data Standards Library (IDSL) will be applied for reporting, unless otherwise stated (IDSL Standards Location: https://spope.gsk.com/sites/IDSLLibrary/SitePages/Home.aspx):           
 
4.03 to 4.23: General Principles
 
5.01 to 5.08: Principles Related to Data Listings
 
6.01 to 6.11: Principles Related to Summary Tables
 
7.01 to 7.13: Principles Related to Graphics
 
 
 
Do not include subject level listings in the main body of the GSK Clinical Study Report. All subject level listings should be located in the modular appendices as ICH or non-ICH listings
 

Formats

 
GSK IDSL Statistical Principles (5.03 & 6.06.3) for decimal places (DP's) will be adopted for reporting of data based on the raw data collected, but may be adjusted to a clinically interpretable number of DP's.
 

Planned and Actual Time

 
Reporting for tables, figures and formal statistical analyses:           
 
Planned time relative to dosing will be used in figures, summaries, statistical analyses and calculation of any derived parameters, unless otherwise stated.
 
The impact of any major deviation from the planned assessment times and/or scheduled visit days on the analyses and interpretation of the results will be assessed as appropriate.
 
 
 
Reporting for Data Listings:           
 
Planned and actual time relative to study drug dosing will be shown in listings (Refer to IDSL Statistical Principle 5.05.1).
 
 
 

Unscheduled Visits

 
Unscheduled or unplanned readings will be presented within the subject's listings.
 
Visits outside the protocol defined time-windows (ie. recorded as protocol deviations) will be included in listings but omitted from figures, summaries and statistical analyses.
 

Descriptive Summary Statistics	
Continuous Data	Refer to IDSL Statistical Principle 6.06.1
Categorical Data	N, n, frequency, %
Graphical Displays	
• Refer to IDSL Statistical Principals 7.01 to 7.13.	

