7.1. Time and Events Table

Visits and Assessments	Screening (up to 4 weeks)	Baseline	Week 4 (±7 days)	Week 8 (±7 days)	Week 12 (±7 days)	Week 16 (±7 days)	Week 20 (±7 days)	Week 24 (±7 days)	Every 4 week treatment cycle/assessments repeated until End of Treatment	Early withdrawal ³	End of Treatment ^{3/} Follow-up (12 weeks post-last dose)
Application Form sent to GSK for approval	X										
Written Informed Consent	X										
Demography and CV risk assessment	X										
Eligibility assessment: inclusion & exclusion criteria review	X										
Baseline information		X									
Dosing with mepolizumab ^{1,2}		X	X	X	X	X	X	X			
Corticosteroid use	X	X	X	X	X	X	X	X		X	X
AE/SAE review	X	X	X	X	X	X	X	X		X	X
Urine pregnancy test (FCBP)	X	X	X	X	X	X	X	X		X	X
Documentation of Benefit:risk evaluation to support continued supply of mepolizumab ¹	X	X			X			X			

1. The treating physician should make a benefit:risk evaluation to confirm continued treatment with mepolizumab is appropriate prior to each administration. This will be documented every 12 weeks to support continued supply. Note: it is expected that the treating physician will monitor subjects as per standard-of-care therapy (including any requirements for blood and urine tests).
2. Safety monitoring of subjects is required during SC administration and for 1 hour after the end of the injections for the first three administrations, i.e., at baseline, and Weeks 4 and 8. From Week 12 onwards, subjects can be monitored following mepolizumab administration in accordance with standard of care at the site.
3. See Section 5.3

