## 1. INTRODUCTION

The purpose of this reporting and analysis plan (RAP) is to describe the analyses and planned outputs to be included in the Clinical Study Report for the Long-term Access Programme (LAP) for mepolizumab in EGPA. The LAP comprises a clinical trial (MEA116841) and compassionate use programme (201607). This document also describes the planned outputs to be included in periodic interim analyses, conducted after the effective date of this RAP, as appropriate

This RAP is based on MEA116841 study protocol amendment 4 issued 18-Jun-2019 (GlaxoSmithKline Document Number [2014N201870\\_04](#)) and has been amended following the previous RAP version which has been used to provide the analyses required for the previous Interim Clinical Study Report (ICSRs).

The clinical data base for the LAP consists of the following subjects:

- Subjects recruited into study MEA116841
- Subjects recruited as part of the named patient supply guidance program 201607

Available data from the above subjects will be included in the analyses specified in this RAP. Combined summaries will be produced from the clinical trial data base for MEA116841 and the NPS guidance program.

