## 9.5. Appendix 5: Reporting Standards for Missing Data

### 9.5.1. Premature Withdrawals

Element	Reporting Detail
General	All available data from subjects in the Safety population who withdrew from mepolizumab will be listed and all available planned data will be included in summary tables and figures, unless otherwise specified.

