## CONFIDENTIAL

MEA116841

Study Population Tables					
No.	Population	IDSL / Example Shell	Title	Programming Notes	Deliverable [Priority]
1.7.	All Subjects Enrolled	DM11	Summary of Age Ranges	
 
MEA116841
 
201607
 
MEA116841 + 201607
 
	IA , SAC
1.8.	Safety	DM5	Summary of Race and Racial Combinations	
 
MEA116841
 
201607
 
MEA116841 + 201607
 
	IA , SAC
1.9.	Safety	mid_mepo_egpa_lap /interim1 Table 1.10	Summary of Race and Racial Combinations Details	
 
MEA116841
 
201607
 
MEA116841 + 201607
 
	IA , SAC
1.10.	Safety	mid_mepo_egpa_lap /interim1 Table 1.11	Summary of Cardiovascular Assessments – Screening Questions	
 
MEA116841
 
201607
 
MEA116841 + 201607
 
	IA , SAC
1.11.	Safety	mid_mepo_egpa_lap /interim1 Table 1.12	Summary of Cardiovascular Assessments – Family History	
 
MEA116841
 
201607
 
MEA116841 + 201607
 
	IA , SAC
1.12.	Safety	mid_mepo_egpa_lap /interim1 Table 1.13	Summary of Oral Corticosteroid Therapy Taken Before the Treatment Period	
 
MEA116841
 
201607
 
MEA116841 + 201607
 
	IA , SAC
1.13.	Safety	mid_mepo_egpa_lap /interim1 Table 1.14	Summary of Oral Corticosteroid Therapy Taken During the Treatment Period	
 
MEA116841
 
201607
 
MEA116841 + 201607
 
	IA , SAC

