### 9.7.5. Safety Tables

Safety: Tables					
No.	Population	IDSL / Example Shell	Title	Programming Notes	Deliverable [Priority]
Exposure					
3.1.	Safety	mid_mepo_egpa_lap /interim1 Table 3.1	Summary of Exposure to Study Treatment	
 
MEA116841
 
201607
 
MEA116841 + 201607
 
	IA , SAC
3.2.	Safety	mid_mepo_egpa_lap /interim1 Table 3.2	Summary of Number of Treatment Administered	
 
MEA116841
 
201607
 
MEA116841 + 201607
 
	IA , SAC
Adverse Events (AEs)					
3.3.	Safety	AE1	Summary of On-Treatment Adverse Events by System Organ Class and Preferred Term	
 
MEA116841
 
201607
 
	IA , SAC
3.4.	Safety	AE1	Summary of Post-Treatment Adverse Events by System Organ Class and Preferred Term	
 
MEA116841
 
201607
 
	IA , SAC
3.5.	Safety	AE3	Summary of Common (>=3%) Adverse Events by Preferred Term	
 
MEA116841
 
201607
 
	IA , SAC
3.6.	Safety	AE1	Summary All Drug-Related Adverse Events by System Organ Class and Preferred Term	
 
MEA116841
 
201607As 3.1 notes
 
	IA , SAC
3.7.	Safety	AE3	Summary of Adverse Events Leading to Permanent Discontinuation of Study Treatment or Withdrawal from Study by Preferred Term	
 
MEA116841
 
201607For studies with few events/participants, listing is sufficient.
 
	IA , SAC

Safety: Tables					
No.	Population	IDSL / Example Shell	Title	Programming Notes	Deliverable [Priority]
3.8.	Safety	AE15	Summary of Common (>=3%) Non-serious Adverse Events by System Organ Class and Preferred Term (Number of Participant and Occurrences)	
 
MEA116841
 
201607Common' to be defined by study/project team. For studies with very few events/participants, listing is sufficient: discuss this option with your disclosure representative.
 
	IA , SAC
3.9.	Safety	AE5A	Summary of On-Treatment Adverse Events by System Organ Class and Preferred Term and Maximum Intensity	
 
MEA116841
 
201607Common' to be defined by study/project team. For studies with very few events/participants, listing is sufficient: discuss this option with your disclosure representative.
 
	IA , SAC

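### The SAP's out-of-window rule omits whole visits from summaries without exempting dosing data, so a late dose that was given could go uncounted and, if last, shorten exposure and the on-treatment window

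*SAP*

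**What the plan says.** Under Unscheduled Visits, SAP 9.3.2 (Reporting Standards) says: "Visits outside the protocol defined time-windows (ie. recorded as protocol deviations) will be included in listings but omitted from figures, summaries and statistical analyses". It gives no exception by data type.

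Two other statements bear on the same data. SAP 1 (Introduction) says: "Available data from the above subjects will be included in the analyses specified in this RAP". Earlier in 9.3.2, under Planned and Actual Time, a separate bullet calls for judging how major timing deviations affect the results; that bullet does not mention omission.

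The Time and Events Table (Protocol 7.1, repeated in SAP 9.1.1) prints ±7 days for Weeks 4, 8, 12, 16, 20 and 24, and up to 4 weeks for screening. The later column, "Every 4 week treatment cycle/assessments repeated until End of Treatment", has no window, and neither does the 12-week follow-up.

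Displays that could be reached include Table 3.2, "Summary of Number of Treatment Administered", and Table 1.13, "Summary of Oral Corticosteroid Therapy Taken During the Treatment Period". The first is a Safety table (SAP 9.7.5) and the second a Study Population table (SAP 9.7.4).

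**The concern.** A rule of this kind suits measurements summarised at nominal visits, where a reading taken far from its target day can blur the time point. This SAP lists no table or listing titled by visit, and no figures. What happens at the visits is dosing, recording of corticosteroid use and review of adverse events, with cardiovascular risk collected at screening only. A dose given on day +8 has still been given, and leaving it out makes the count wrong.

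The programme has no hypotheses, and its product is a set of descriptive safety summaries. At stake are agreement between Table 3.2 and the exposure listing (Listing 9), the exposure in Table 3.1, and the boundary between on-treatment and post-treatment events. That boundary and the exposure both feed the exposure-adjusted tables (3.42 to 3.46).

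**Working it through.** The plan gives no figure on this point, so there is none to reproduce. The check is one worked subject, a range for the size, and a comparison of the texts.

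**1. One hypothetical subject**

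Inputs:
- Dosing every 4 weeks (Protocol 7.1), so scheduled doses from baseline to Week 24 fall on Days 1, 29, 57, 85, 113, 141 and 169: 7 doses.
- Exposure in days = stop date − start date + 29 (SAP 9.4.2).
- On-treatment runs to stop date + 28 days (SAP 9.2.1).
- Assumed: the Week 24 dose is the last and is given 10 days late, on Day 179. This is outside ±7 days and is recorded as a deviation.
- Assumed: the stop date is taken from the dosing records that remain after the rule is applied.

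| | Doses counted | Exposure (days) | On-treatment ends |
|---|---|---|---|
| All doses on time | 7 | 169 − 1 + 29 = 197 | Day 169 + 28 = 197 |
| Late last dose kept | 7 | 179 − 1 + 29 = 207 | Day 179 + 28 = 207 |
| Late last dose omitted | 6 | 141 − 1 + 29 = 169 | Day 141 + 28 = 169 |

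Omission removes 1 of 7 doses and 207 − 169 = 38 days. An event starting on Days 170 to 207 would move from on-treatment to post-treatment.

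If instead only the Week 12 dose (Day 85) were omitted, the count would fall from 7 to 6. Duration would stay at 169 − 1 + 29 = 197 days, because the formula uses only the first and last dates. It would change only if the gap were treated as a treatment break, for which SAP 9.4.2 adjusts exposure.

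**2. Size, on printed windows only**

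Six post-baseline dosing visits carry a ±7 day window. The documents give no out-of-window rate, so the rates are assumed. Expected doses lost per subject = 6 × rate:

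- 5%: 6 × 0.05 = 0.3
- 10%: 6 × 0.10 = 0.6
- 20%: 6 × 0.20 = 1.2

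As a share of the first 7 doses, these are 0.3/7 = 4.3%, 0.6/7 = 8.6% and 1.2/7 = 17.1%. After Week 24 no window is printed, so being outside a protocol-defined window has no stated meaning there.

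**3. The texts side by side**

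- The Introduction puts available data into the analyses without qualification. The 9.3.2 rule takes some of it out.
- One bullet in 9.3.2 has the impact of major timing deviations assessed. The later bullet removes the visits, so their impact on the summaries could not be seen there.
- The rule turns on visits being recorded as protocol deviations. The deviation displays (Table 1.4, Listings 4 and 5) cover MEA116841 only, and SAP 7 says the sponsor did not monitor 201607. Tables 1.10 to 1.13, 3.1 and 3.2 nevertheless have a combined column, which could mix filtered and unfiltered records.

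**The case against.** The best defence is that the sentence is a generic reporting convention. It sits next to a bullet on unscheduled readings and refers to figures and statistical analyses that this SAP hardly contains. It also reaches only visits recorded as deviations. SAP 4.1 leaves that recording to a separate management plan not included here, and the important deviations it names do not include visit timing. All of this stands as a reason to expect the rule to apply seldom. It does not exempt dosing data, and a convention with no evident use here loses nothing by being narrowed.

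Four stronger readings are tempting, and the documents do not support them:

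- **That SAP 9.5.1 is contradicted.** That section covers only subjects who withdrew from treatment, and its promise about summaries reads: "all available planned data will be included in summary tables and figures, unless otherwise specified". It is limited to planned data and yields to other text, which 9.3.2 could be.
- **That adverse events vanish when reported at a late visit.** SAP 7.1 and 9.2.1 classify events by onset and treatment dates. The route to harm is through the stop date, not the reporting visit.
- **That corticosteroid records are lost in proportion to late visits.** SAP 9.5.2.1 handles concomitant medication by start and stop dates, so a dated course need not depend on one visit. The shells for Tables 1.10 to 1.13 are not in the documents. For the cardiovascular tables, up to 4 weeks may describe the length of screening rather than a window. An effect on these Study Population tables is possible but not shown. Among Safety tables, cardiovascular risk enters by title only at Table 3.32.
- **That the loss accumulates over the whole programme.** Carrying ±7 days forward over 104 weeks (104/4 = 26 post-baseline doses) would give 1.3, 2.6 or 5.2 doses at the same rates. That is 26/6 = 4.3 times what the printed windows support.

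**Conclusion.** The concern holds in a limited form. As written, the rule can remove doses that were given from Table 3.2 and, when the late dose is the last, shorten both exposure and the on-treatment window (by 38 days in the example). The expected loss is about 0.3 to 1.2 doses per subject at assumed rates of 5% to 20% over Weeks 4 to 24.

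This rests on a literal application of the rule, on late visits being recorded as deviations and, for duration, on the stop date coming from the filtered records. The direction of any effect on exposure-adjusted rates is not fixed, because numerator and denominator can both fall. That visits slip when subjects are unwell is a reasonable judgement, but the documents do not establish it. No hypothesis test is affected. The change should be made because the rule gives a wrong count when followed and has no evident purpose among the listed displays.

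**What to change.** Delete the sentence in SAP 9.3.2. Alternatively, keep it and add that it does not apply to dosing, exposure, corticosteroid, cardiovascular-risk, demography or adverse event data, which are summarised whatever the visit timing.

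Identify out-of-window visits in the data listings themselves, for example Listing 9. The deviation listing alone will not do, since Listing 4 covers important deviations in MEA116841 only. SAP 9.3.2 already calls for planned and actual times in listings.

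If any form of the rule is kept, state which windows apply after Week 24 and how it is applied to 201607, so that combined columns are built one way.

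The cost is one sentence in the SAP, with no new data and little or no programming.

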## 9.4. Appendix 4: Derived and Transformed Data

### 9.4.1. General

Study Day

 
Calculated as the number of days from First treatment:           
 
Ref Date = Missing → Study Day = Missing
 
Ref Date < Date of first treatment → Study Day = Ref Date – Date of first treatment
 
Ref Date ≥ Date of first treatment → Study Day = Ref Date – (Date of first treatment) + 1
 
 
 

### 9.4.2. Study Population

Extent of Exposure

 
Number of days of exposure to study drug will be calculated based on the formula:  Duration of Exposure in Days = Treatment Stop Date – (Treatment Start Date) + 29 
 
Participants who were randomized but did not report a treatment start date will be categorised as having zero days of exposure.
 
If there are any treatment breaks during the study, exposure data will be adjusted accordingly.
 

### 9.4.3. Safety

Adverse Events
Drug Related AEs
AEs with relationship marked 'YES'.
AEs Leading to Permanent Discontinuation from Study Treatment or Withdrawal from the Study
AEs with action marked "Study treatment withdrawn" or withdrawn from study status marked "YES", or a response to either of these questions is missing.
AEs on Day of Dosing
AEs with an onset date equal to a study treatment dosing date and an onset time on or after the study treatment dosing time.
AE Time Since First Dose

 
If AE onset time is missing, calculate in days as follows:-           
 
If AE start date < Date of first dose of study treatment then  <math display="block">\text{Time since first dose} = \text{AE start date} - \text{Date of first dose of study treatment}</math> 
 
If AE start date ≥ Date of first dose of study treatment then  <math display="block">\text{Time since first dose} = \text{AE start date} - \text{Date of first dose of study treatment} + 1</math> 
 
Missing if AE start date or date of first dose of study treatment is missing.
 
 
 
If AE onset time is present, calculate in days, hours, minutes as  <math display="block">\text{Time since first dose} = \text{AE start date/time} - \text{Date/time of first dose of study treatment}</math> 
 

AE Duration (Days)

• If AE onset time is missing, calculate in days as AE end date – AE start date + 1

• If AE onset time is present, calculate in days, hours and minutes as AE end date/time – AE start date/time

• Missing if AE start date or end date is missing.

AEs of Special Interest

• See Section 7.2.

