12.4.5. Evaluating Aes and SAEs

Assessment of Intensity

The investigator will make an assessment of intensity for each AE and SAE reported during the study and will assign it to one of the following categories:

- Mild: An event that is easily tolerated by the subject, causing minimal discomfort and not interfering with everyday activities.
- Moderate: An event that is sufficiently discomforting to interfere with normal everyday activities
- Severe: An event that prevents normal everyday activities. – an AE that is assessed as severe will not be confused with an SAE. Severity is a category utilized for rating the intensity of an event; and both Aes and SAEs can be assessed as severe.
- An event is defined as 'serious' when it meets at least one of the pre-defined outcomes as described in the definition of an SAE.

Assessment of Causality

- The investigator is obligated to assess the relationship between study treatment and the occurrence of each AE/SAE.
- A “reasonable possibility” is meant to convey that there are facts/evidence or arguments to suggest a causal relationship, rather than a relationship cannot be ruled out.
- The investigator will use clinical judgment to determine the relationship.
- Alternative causes, such as natural history of the underlying diseases, concomitant therapy, other risk factors, and the temporal relationship of the event to the study treatment will be considered and investigated.
- The investigator will also consult the Investigator Brochure (IB) and/or Product Information, for marketed products, in the determination of his/her assessment.
- For each AE/SAE the investigator **must** document in the medical notes that he/she has reviewed the AE/SAE and has provided an assessment of causality.
- There may be situations when an SAE has occurred and the investigator has minimal information to include in the initial report to GSK. However, **it is very important that the investigator always make an assessment of causality for every event prior to the initial transmission of the SAE data to GSK.**
- The investigator may change his/her opinion of causality in light of follow-up information, amending the SAE data collection tool accordingly.
- The causality assessment is one of the criteria used when determining regulatory reporting requirements.

Follow-up of AEs and SAEs

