## 7. SAFETY ANALYSES

The safety analyses will be based on the Safety population, unless otherwise specified.

The LAP comprises a clinical trial (MEA116841) and compassionate use programme (201607) restricted to subjects who participated in MEA115921. The compassionate use programme (CUP) was conducted under a guidance document which mirrored the objectives of MEA116841. Since 201607 was run as a CUP, the treating physician was the responsible party. Per local legal requirements, serious adverse event reporting was required at a minimum. Furthermore, GSK did not monitor CUP 201607, and therefore verification that all non-serious adverse events (AEs) were reported is not possible.

For this reason, summaries of adverse events are reported separately for MEA116841 and 201607, with the exception of serious adverse events, which are additionally reported using combined MEA116841 and 201607 data.

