### 9.5.2. Handling of Missing Data

Element	Reporting Detail
General	
 
Missing data occurs when any requested data is not provided, leading to blank fields on the collection instrument : 
 
These data will be indicated by the use of a "blank" in subject listing displays. Unless all data for a specific visit are missing in which case the data is excluded from the table.
 
Answers such as "Not applicable" and "Not evaluable" are not considered to be missing data and should be displayed as such.
 
 
 

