3.16.	Safety	AE1	Summary of Drug-Related Non-Fatal Serious Adverse Events by System Organ Class and Preferred Term	
 
MEA116841
 
201607For studies with few events/participants listing is sufficient: discuss this option with your disclosure representative.
 
MEA116841 + 201607
 
	IA , SAC

Safety: Tables					
No.	Population	IDSL / Example Shell	Title	Programming Notes	Deliverable [Priority]
3.17.	Safety	AE1	Summary of Drug-Related Fatal Adverse Events by System Organ Class and Preferred Term	
 
MEA116841
 
201607For studies with few events/participants listing is sufficient: discuss this option with your disclosure representative.
 
MEA116841 + 201607
 
	IA , SAC
3.18.	Safety	AE3	Summary of Non-Serious Drug-Related Adverse Events by Overall Frequency	
Required for Plain Language Summary
 
 
MEA116841
 
201607For studies with few events/participants listing is sufficient: discuss this option with your disclosure representative.
 
MEA116841 + 201607
 
	IA , SAC
3.19.	Safety	AE3	Summary of Serious Drug-Related Adverse Events by Overall Frequency	
Required for Plain Language Summary
 
 
MEA116841
 
201607For studies with few events/participants listing is sufficient: discuss this option with your disclosure representative.
 
MEA116841 + 201607
 
	IA , SAC

Safety: Tables					
No.	Population	IDSL / Example Shell	Title	Programming Notes	Deliverable [Priority]
3.20.	Safety	mid_mepo_egpa_lap /interim1 Table 3.16	Summary of All Cardiovascular Events Reported by the Investigator	
 
MEA116841
 
201607 For studies with few events/participants listing is sufficient: discuss this option with your disclosure representative.
 
MEA116841 + 201607
 
	IA , SAC
Adverse Events of Special Interest					
3.21.	Safety	mid_mepo_egpa_lap /interim1 Table 3.17	Summary of On-Treatment Adverse Events of Special Interest: Systemic Reactions	
 
MEA116841
 
201607
 
	IA , SAC

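### SAP 9.4.3 counts an AE as drug-related only if relationship is 'YES' and has no rule for a missing answer, so any blank left at a data cut drops out of the drug-related tables, which could then be too low

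*SAP*

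**What the plan says.** SAP 9.4.3 gives one criterion for a drug-related event: "AEs with relationship marked 'YES". It has no clause for a missing response. The definition directly after it, for AEs leading to permanent discontinuation or withdrawal, includes an event if the relevant box is marked "or a response to either of these questions is missing".

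The general missing-data text does not fill the gap. SAP 9.5.2 says that missing items appear as blanks in subject listings. SAP 9.5.2.1 sets conventions only for AE and concomitant medication dates.

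The drug-related definition feeds Table 3.6 (all drug-related AEs), Tables 3.16 and 3.17 (drug-related non-fatal SAEs and fatal AEs), Table 3.18 (non-serious), Table 3.19 ("Summary of Serious Drug-Related Adverse Events by Overall Frequency") and Table 3.44 (exposure-adjusted). Tables 3.18 and 3.19 are marked as needed for the plain language summary. Tables 3.22 and 3.27 split systemic and injection-site reactions by relatedness.

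Protocol 12.4.5 expects the field to be filled: "The investigator is obligated to assess the relationship between study treatment and the occurrence of each AE/SAE". For SAEs it adds that "it is very important that the investigator always make an assessment of causality for every event prior to the initial transmission of the SAE data".

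**The concern.** A rule that admits only 'YES' has a default built into it: an event with no answer is not counted as drug-related. The SAP's other AE classification rules lean the other way when data are missing. A missing answer counts as a discontinuation event (9.4.3). A missing or partial onset date is on-treatment unless there is evidence to the contrary (7.1). A missing treatment stop date makes the event on-treatment (9.2.1 and its note). Causality alone defaults to the favourable side, and no reason is given.

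The affected outputs are safety tables for an open-label programme whose interim analyses exist to inform the risk-benefit assessment (Protocol 9.1) and may go to regulators (SAP 3.1). SAP 3.2 requires cleaning to be complete before the final analysis; SAP 3.1 states no matching step for an interim cut. Any blank that survives to a cut lowers the drug-related counts, and the plan provides no table footnote to show that this happened.

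**Working it through.** There is no planned figure to reproduce: the documents give no drug-related count, no blank rate and no sample size for the access programme. The check is a reading of the rules followed by a bounding calculation on assumed inputs.

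**1. What happens to a blank**

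| Place | Treatment of a missing answer |
|---|---|
| SAP 9.4.3, drug-related | none stated; only 'YES' qualifies |
| SAP 9.4.3, discontinuation or withdrawal | counted as an event |
| SAP 7.1, onset date | on-treatment unless there is contrary evidence |
| SAP 9.2.1 note, treatment stop date | on-treatment |
| SAP 9.5.2 and 9.5.2.1 | blank in listings; only dates imputed |

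On the text available, a blank relationship is therefore absent from Tables 3.6, 3.16 to 3.19 and 3.44. For Tables 3.22 and 3.27 its place is unspecified.

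**2. Effect on the share of AE records shown as drug-related**

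Let *m* be the share of AE records with a blank relationship and *r* the related share among completed records. Both are assumptions.

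- YES-only share = (1 − m) × r
- Share with blanks counted as related = (1 − m) × r + m
- If blanks are independent of relatedness, the true share is r, so the relative understatement is [r − (1 − m)r] / r = m

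| m | r = 5%: YES-only | r = 5%: blanks counted | r = 20%: YES-only | r = 20%: blanks counted |
|---|---|---|---|---|
| 0% | 5.0% | 5.0% | 20.0% | 20.0% |
| 1% | 4.95% | 5.95% | 19.8% | 20.8% |
| 5% | 4.75% | 9.75% | 19.0% | 24.0% |
| 10% | 4.5% | 14.5% | 18.0% | 28.0% |

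If none of the blank events was truly related, the YES-only count is correct even though blanks exist.

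**3. Effect at subject level**

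One affected subject moves an incidence by 100/N percentage points. The parent study randomises 130 subjects (Protocol 2.2). Taking that as the ceiling, the shift is at least 100/130 = 0.77 points. It is 1.0 point at N = 100 and 2.0 points at N = 50 (assumed sizes). In a rare category such as Table 3.17, one blank on a truly related death turns a count of 1 into 0.

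**4. Is counting blanks as related more accurate?**

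Assume 200 AEs, 30 truly related, and 10 blanks unconnected with relatedness.

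- YES-only, expected: 30 × (1 − 10/200) = 28.5, an error of −1.5
- Blanks counted as related: 28.5 + 10 = 38.5, an error of +8.5

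More generally, with B blanks of which a share q is truly related, the errors are −Bq and +B(1 − q). Counting blanks is closer to the truth only when q exceeds one half. It is a cautious convention, not a better estimate.

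**The case against.** The best counter-argument is that blanks should be rare. In MEA116841 the investigator must assess causality for each AE and SAE and must record in the medical notes that this was done (Protocol 12.4.5). Protocol 8 provides for data cleaning and is not limited to the final analysis, and under Protocol 10.2 monitors verify completeness. SAEs and deaths are the least likely places for a blank in that study. Listings 11, 14 and 15 cover all AEs and the fatal and non-fatal SAEs, and SAP 9.5.2 says blanks appear in listings. The sponsor's reporting standards (SAP 9.3.2) or the earlier interim shells, neither available here, might already hold a default or a missing row.

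Much of this stands. It bears on how often the gap bites, but it does not close it. The standards apply only unless otherwise stated, and 9.4.3 states a definition. Listings are kept out of the main report body, and whether they show relationship depends on shells not seen here. The protocol duties are those of MEA116841; the guidance document for 201607 is not available.

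Three stronger readings are tempting, and the documents do not support them:

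- **A reader might infer that blanks are tabulated as unrelated.** The SAP does not say so; they are only left out of the drug-related tables.
- **A reader might take "GSK did not monitor CUP 201607" as evidence of blank causality fields.** That sentence of SAP 7 goes on to unverified reporting of non-serious AEs, meaning events never reported rather than unanswered fields in reported ones. Blanks are more plausible in unmonitored data, but that is judgement. Tables 3.22, 3.27 and 3.44 are produced by programme, so 201607 blanks would not enter their MEA116841 results; Tables 3.16 to 3.19 also pool the two.
- **A reader might think a blank could not be recovered.** In MEA116841 the required entry in the medical notes gives a source to query.

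**Conclusion.** The point holds as a gap with a known direction and an unknown size. The drug-related definition is YES-only, has no missing-response clause, and is inconsistent with the definition beside it and with the SAP's other AE defaults. Any effect on Tables 3.6, 3.16 to 3.19 and 3.44 can only be downward. Placement in Tables 3.22 and 3.27 is undefined.

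The documents do not show that drug-related events, SAEs or deaths are in fact understated, because they report no blank relationship field. With no blanks, or with no related event among them, the effect is zero. The relative shortfall equals the blank share only if blanks are independent of relatedness; the 1%, 5% and 10% used above are assumptions. Confidence is high in the gap and its direction, and low in any particular magnitude. A change is still warranted because the rule errs only in the favourable direction, some outputs go into a public summary, and the remedy is cheap.

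**What to change.** Before the next interim cut or the database freeze:

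1. Query every blank relationship field to resolution.
2. In SAP 9.4.3, define drug-related as relationship 'YES' or still missing after query, in line with the adjacent definition.
3. In Tables 3.6, 3.16 to 3.19 and 3.44, footnote separately for MEA116841 and 201607 how many events were counted only because the field was blank. The YES-only count can then be recovered.
4. In Tables 3.22 and 3.27, show missing explicitly.

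The cost is one line in the SAP, a footnote, an added display category and the query effort. If no blanks remain, no count changes. If some do, the drug-related counts become conservative and may exceed the true number, possibly by more than the present rule falls short. The blank counts by programme are therefore an essential part of the change.
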